### **2.3 Quality of Life Objective**

The quality of life objective will be to determine the impact of the addition of atezolizumab to FOLFOX on patient-reported neuropathy, health-related QOL, and functional domains of health-related QOL. The quality of life analysis will also assess the efficacy of atezolizumab

adjusting for baseline QOL and fatigue measurements. Patient-reported outcomes will not be assessed in patients aged 12 to <18 years.

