\*\*\* Patients will be followed for recurrence every 6 months (+/- 1 month) for the first two years after registration, and then once annually (+/- 1 month) for years 3-5 after registration. Recurrence follow-up will continue per the schedule above for 5 years after registration or until evidence of relapse, whichever comes first. See [Section 12.0](#) for survival follow-up.

- 1 For patients aged 12 to <18 years. Staging should be performed until the patient has reached Tanner Stage V.
- 2 Oxygen saturation should be assessed at rest and after 1 minute walk.
- 3 Solicited AEs are to be collected starting prior to treatment until off-treatment (see [Section 9.1](#)). Routine AEs are to be collected starting after registration until the end of survival follow-up. For patients who complete one cycle of FOLFOX prior to registration, the first routine AE assessment should take place after registration but prior to Day 1 Cycle 2 of FOLFOX; see [Section 9.3](#) for expedited SAE reporting.
- 4 Patients aged  $\geq 18$  years complete PRO-CTCAE by paper booklet ordered through the CTSU website. See [Section 9.1](#) for administration instructions. See [Appendix I](#) for PRO-CTCAE assessments for IRB submission and review only. See [Section 4.3](#) for ordering instructions. PRO-CTCAE booklets should be administered at the following time points:  $\leq 14$  days prior to registration; Day 1 of each Cycle, and at the end of treatment.
- 5 To be completed after registration but  $\leq 21$  days prior to treatment. See [Appendix I](#).
- 6 Albumin, alkaline phosphatase, total bilirubin, bicarbonate (or total CO2), BUN, calcium, chloride, serum creatinine, glucose, potassium, total protein, SGOT (AST), SGPT (ALT), and sodium.
- 7 Perform at baseline and then every 8 weeks (+/- 14 days).
- 8 For women of childbearing potential ([Section 3.2.6](#)). Must be done  $\leq 7$  days prior to registration.
- 9 Perform at baseline, 6 weeks (+/- 7 days) after end of FOLFOX, then every 6 months (+/- 1 month) for 3 years, then every 12 months (+/- 1 month) for an additional 2 years, or until relapse. After the end of FOLFOX treatment, the timing of CEA testing should correspond with timing of radiographic imaging studies, where possible, but more frequent testing is at provider discretion.
- 10 HIV-positive patients should complete a CD4 count and viral load  $\leq 28$  days prior to registration.

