**6.4 Quality of Life Assessments**

Patient-completed questionnaire booklets for this study are to be ordered prior to the registration of any patients (see [Section 4.3](#)). Samples of questionnaire booklets are available in [Appendix I](#) for reference and IRB submission only. They are not to be used for patient completion. Booklets must be given to patients to complete and patients should be instructed to return the booklets to site staff in person and site staff will enter patient responses into Rave. At visits in which booklets are to be completed, the booklet should be given to the patient before any discussion of the patient's health status or test results. Booklet administration schedule is provided below. Please note that PRO-CTCAE is contained in a separate booklet and is required for all patients 18 years or older per the study calendar. The schedule below only pertains to patients aged  $\geq 18$  years who consent to participate in the Quality of Life study.

ARM 1: mFOLFOX6 + atezolizumab	≤ 14 Days Prior to Registration	Prior to Cycles 4, 7, & 13 (+/-3 days)	End of Treatment Visit (+/-7 days)	3 Years after Registration (+/-28 days)
For patients registered to A021502-HO1, submit patient-completed questionnaires* at the following time points:				
	X	X	X	X

ARM 2: mFOLFOX6	≤ 14 Days Prior to Registration	Prior to Cycles 4 & 7 (+/-3 days)	End of Treatment Visit (+/-7 days)	12 Months after Registration (+/-14 days)	3 Years after Registration (+/-28 days)
For patients registered to A021502-HO1, submit patient-completed questionnaires* at the following time points:					
	X	X	X	X	X

\*See [Appendix I](#) for FACT-C, FACT/GOG-NTX, and EQ-5D-5L questionnaires for IRB submission and review only. Patients must complete the questionnaires in booklet format. See [Section 4.3](#) for ordering instructions.

Submission of Completed Booklets: The data from the booklets are to be entered into Medidata Rave by site staff. Data entry should correlate with the cycles notes in the above schedules (e.g. entered within Cycles 4, 7, or 13).

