## 9.0 ADVERSE EVENTS

The prompt reporting of adverse events is the responsibility of each investigator engaged in clinical research, as required by Federal Regulations. Beginning April 1, 2018, adverse events must be described and graded using the terminology and grading categories defined in the NCI's Common Terminology Criteria for Adverse Events (CTCAE), Version 5.0. The CTCAE is available at [ctep.cancer.gov/protocolDevelopment/electronic\\_applications/ctc.htm](http://ctep.cancer.gov/protocolDevelopment/electronic_applications/ctc.htm). Attribution to protocol treatment for each adverse event must be determined by the investigator and reported on the required forms. Please refer the NCI Guidelines: Adverse Event Reporting Requirements for further details on AE reporting procedures.

To complement CTCAE reporting, patients aged  $\geq 18$  years will self-report their side effects using the PRO-CTCAE. The specific PRO-CTCAE items for this protocol can be found in [Appendix I](#). They can also be found at: <http://healthcaredelivery.cancer.gov/pro-ctcae/instrument.html>.

**NOTE:** PRO-CTCAE data should not be used for determining attribution, dose modifications, or reporting of serious adverse events.

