**9.1.2 Solicited Adverse Events**

The following adverse events are considered "expected" and their presence/absence should be solicited, and severity graded, at baseline and for each cycle of treatment by CTCAE, PRO-CTCAE, or both.

**NOTE:** PRO-CTCAE data should not be used for determining attribution, dose modifications, or reporting of serious adverse events.

CTCAE v5.0 Term	PRO-CTCAE v1.0 Term	CTCAE v5.0 System Organ Class (SOC)
The following adverse events should be solicited at baseline and for each treatment cycle:		
Hypothyroidism		Endocrine disorders
Abdominal Pain	Pain in the abdomen (belly area)	Gastrointestinal disorders
Constipation	Constipation	Gastrointestinal disorders
Nausea	Nausea	Gastrointestinal disorders
Fatigue	Fatigue, tiredness, or lack of energy	General disorders and administration site conditions
Anorexia	Decreased appetite	Metabolism and nutrition disorders
Cough	Cough	Respiratory, thoracic, and mediastinal disorders
Dyspnea	Shortness of breath	Respiratory, thoracic, and mediastinal disorders
Fever		General disorders
Blood bilirubin increased		Investigations
Neutrophil count decreased		Investigations
Platelet count decreased		Investigations
	Loose or watery stools (diarrhea)	Gastrointestinal disorders
	Vomiting	Gastrointestinal disorders
	Numbness or tingling in your hands or feet	Nervous system disorders

CTCAE v5.0 Term	PRO-CTCAE v1.0 Term	CTCAE v5.0 System Organ Class (SOC)
	Heartburn	Gastrointestinal disorders
Palmar-plantar erythrodysesthesia syndrome	Hand-foot syndrome (a rash of the hands or feet that can cause cracking, peeling, redness, or pain)	Skin and subcutaneous tissue disorders
	Rash	Skin and subcutaneous tissue disorders
	Itchy skin	Skin and subcutaneous tissue disorders
	Mouth or throat sores	Gastrointestinal disorders
The following adverse events should be solicited as clinically indicated*:		
Alanine aminotransferase increased 		Investigations
Aspartate aminotransferase increased 		Investigations
Hepatitis		Infections and infestations
Encephalitis infection		Infections and infestations
Kidney infection		Infections and infestations
Infective myositis		Infections and infestations
Infections and infestations – Other, specify 		Infections and infestations
Pneumonitis		Respiratory, thoracic, and mediastinal disorders
Colitis		Gastrointestinal disorders
Pancreatitis		Gastrointestinal disorders
Hyperglycemia		Metabolism and nutrition disorders

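### Seven of the 20 events that Section 9.1.2 solicits every cycle have only a PRO-CTCAE term, so no instrument solicits them in patients aged 12 to <18

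*Combined protocol and SAP*

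**What the plan says.** Section 9.1.2 (Solicited Adverse Events) says that the listed events are to be "solicited, and severity graded, at baseline and for each cycle of treatment by CTCAE, PRO-CTCAE, or both". The table beneath has one column of CTCAE terms and one of PRO-CTCAE terms. In the block for baseline and every cycle, the rows "Loose or watery stools (diarrhea", "Numbness or tingling in your hands or feet" and "Mouth or throat sores" have no CTCAE term. Nor do the rows for vomiting, heartburn, rash and itchy skin.

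The age limit on PRO-CTCAE appears in several places:

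- Section 2.3: "Patient-reported outcomes will not be assessed in patients aged 12 to <18 years".
- Section 5.0, study calendar footnote 4: patients aged at least 18 "years complete PRO-CTCAE by paper booklet ordered through the CTSU website".
- Section 6.4: "PRO-CTCAE is contained in a separate booklet and is required for all patients 18 years or older".
- Section 9.0: patients aged at least 18 "years will self-report their side effects using the PRO-CTCAE".
- Sections 2.2 and 13.1.2 carry the same limit.

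One passage reads differently. Section 4.3 describes the PRO-CTCAE booklet as required of all patients, with no age limit, and refers to the study calendar.

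**The concern.** Solicitation differs from collection. A solicited item is asked about at each visit, so a blank or zero means that the symptom was absent. An unsolicited event enters the record only if someone raises it, and silence cannot be read as absence.

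For the seven PRO-only rows, Section 9.1.2 relies wholly on an instrument that adolescents are not given, and it names no substitute for them. Adults have PRO-CTCAE as a solicited source alongside routine CTCAE reporting; adolescents have routine reporting alone. The protocol's drug sections list several of these symptoms as common with the study drugs: diarrhea and vomiting with all three of fluorouracil, oxaliplatin and atezolizumab, and neuropathy with oxaliplatin. Adolescents are randomized (Section 13.2) and, once treated, belong to the safety population (Section 13.0). What is at stake is the quality of the symptom record in a small group of minors.

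**Working it through.** There is no plan figure to reproduce and no formula applies. The check is a row count and a comparison of sections.

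**Step 1: classify the every-cycle rows in Section 9.1.2.**

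| Term given | Events | Count |
|---|---|---|
| CTCAE only | hypothyroidism, fever, bilirubin increased, neutrophils decreased, platelets decreased | 5 |
| Both | abdominal pain, constipation, nausea, fatigue, anorexia, cough, dyspnea, hand-foot syndrome | 8 |
| PRO-CTCAE only | diarrhea, vomiting, numbness/tingling, heartburn, rash, itchy skin, mouth/throat sores | 7 |

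Total: 5 + 8 + 7 = 20.

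**Step 2: check that the table was read correctly.** The PRO-CTCAE terms number 8 + 7 = 15, and the PRO-CTCAE booklet in Appendix I has 15 numbered symptoms. No PRO-CTCAE row has been lost. This supports the blank CTCAE cells only indirectly, but the section's allowance for one instrument or both anticipates single-instrument rows.

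**Step 3: apply the age rule.** Below age 18 only CTCAE remains. Adolescents are solicited for 5 + 8 = 13 of 20 events, and 7 of 20 (35%) are solicited by nothing. Section 4.3 does not change this, because it defers to the study calendar and the calendar footnote sets the limit at 18.

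**Step 4: look for another route.**

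- None of the seven terms reappears in the block solicited when clinically indicated. Colitis is there, but it is not diarrhea at every cycle.
- The hand-foot row covers only rash of the hands and feet.
- Section 4.5 bars adolescents from the quality-of-life substudy, so FACT/GOG-NTX does not cover neuropathy.
- The oxaliplatin neurotoxicity scale in Section 8.2.1.4 guides dose modification and sets no solicitation schedule.

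**Step 5: establish what is still collected.** Section 9.1.1 puts adverse events after the start of treatment on the Adverse Event form each reporting period, and earlier ones on a baseline form. The table in Section 9.2 requires grades 1-2 when at least possibly related and grades 3-5 with any attribution. The remaining loss is a solicited baseline grade, a recorded absence, and grade 1-2 events judged unrelated or unlikely. Section 9.1.1, read literally, covers all events after treatment starts; on that reading the last item shrinks, but absence is still not recorded.

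**The case against.** The strongest reply is that little is missed in practice. History and physical examination are due on Day 1 of each cycle. Section 8.2 bases each new cycle on adverse events since the prior dose and forbids the use of PRO-CTCAE for dose modification. Grade-based rules exist for diarrhea and vomiting (8.2.1.2), mucositis (8.2.1.3), neuropathy (8.2.1.4) and, for atezolizumab, skin events (8.2.2). Clinicians must therefore ask about most of these symptoms; heartburn is the main exception. This stands as a limit on the size of the problem. It does not supply the recorded presence or absence that Section 9.1.2 demands.

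Three stronger readings are tempting, and the documents do not support them.

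- A reader might infer that the plan pools solicited adult data with unsolicited adolescent data. It does not. The CTCAE cells are blank for these rows at every age, so clinician-graded data on them are unsolicited in adults too. Sections 13.1.2 and 13.4.3 record and analyze the two instruments separately, and CTCAE may enter the PRO-CTCAE analysis only as auxiliary imputation data for events captured by both.
- A reader might infer that the leading atezolizumab effects go unsolicited. The risk list in Section 9.4 places diarrhea and rash in its less-likely category (at most 20%). The entries above 20% are fatigue and infection, and fatigue is solicited by CTCAE in adolescents every cycle.
- A reader might infer that toxicity is materially under-ascertained. CTCAE reporting rules are the same at all ages, and Section 9.0 presents PRO-CTCAE as a complement to them.

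It is also fair to say that no planned analysis is shown to suffer. The adolescent objectives (2.4.11 and 2.4.12) concern growth and development, and the stopping rule in Section 13.5 uses deaths within 60 days. The gap applies in both arms, so no between-arm bias is shown.

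**Conclusion.** The point holds as a minor inconsistency with a real, limited effect on data collection. Section 9.1.2 sets a rule that cannot be met for patients aged 12 to <18 on seven of 20 every-cycle events. The conclusion rests on two assumptions: that the blank CTCAE cells are intended, and that the age-specific passages govern over Section 4.3.

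The number of adolescents is not stated and is likely small: Section 1.1 calls the disease rare at this age, and the German sites enrol only from age 18 (Appendix IV, section 1.1). Adolescents are not counted toward the 700. DFS events in adolescents count in the primary analysis, but adverse event solicitation does not bear on them, so the primary endpoint, alpha and power are unaffected.

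**What to change.** In Section 9.1.2, add that for patients aged 12 to <18 the CTCAE counterparts of the seven PRO-only rows are solicited and graded at baseline and each cycle on the existing Adverse Events form. Sections 9.3 and 9.4 already use CTCAE terms for six of them (diarrhea, vomiting, peripheral sensory neuropathy, rash, pruritus, oral mucositis); a term for heartburn has to be chosen.

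Report these adolescent data separately. Adult CTCAE data for the same terms are unsolicited, so merging the two would create the mixture of solicited and unsolicited data that the plan now avoids.

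Bring Section 4.3 into line with the age limit in calendar footnote 4.

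The cost is one sentence and a few form fields for a small subgroup. The documents do not give adolescent accrual status, although Section 13.5 mentions possible re-opening to accrual. If adolescent treatment is already complete, new fields come too late; the plan should then state that non-report of these seven events in adolescents is not a solicited absence.

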## 9.2 CTCAE Routine Reporting Requirements

In addition to the solicited adverse events listed in [Section 9.1](#), the following table outlines the combinations of time points, grades and attributions of AEs that require routine reporting to the Alliance Statistics and Data Center. Questions about routine reporting should be directed to the Data Manager.

**NOTE:** PRO-CTCAE data should not be used for determining attribution, dose modifications, or reporting of serious adverse events.

Combinations of CTCAE Grade & Attribution Required for Routine AE Data Submission on Case Report Forms (CRFs)

Attribution	Grade 1	Grade 2	Grade 3	Grade 4	Grade 5
Unrelated			a	a	a
Unlikely			a	a	a
Possible	a	a	a, b	a, b	a, b
Probable	a	a	a, b	a, b	a, b
Definite	a	a	a, b	a, b	a, b

- a) Adverse Events CRF - Applies to AEs occurring between registration and within 30 days of the patient's last treatment date, or as part of the Clinical Follow-Up Phase.
- b) Late Adverse Events CRF - Applies to AEs occurring greater than 30 days after the patient's last treatment date up to the end of the survival follow-up period.

## 9.3 Expedited Adverse Event Reporting (Rave-CTEP-AERS)

Investigators are required by Federal Regulations to report serious adverse events as defined in the table below. Alliance investigators are required to notify the Alliance Central Protocol Operations Program, the Study Chair, and their Institutional Review Board if a patient has a reportable serious adverse event. The descriptions and grading scales found in the NCI Common Terminology Criteria for Adverse Events (CTCAE) Version 5.0 will be utilized for AE

reporting. The CTCAE is identified and located on the CTEP website at: [ctep.cancer.gov/protocolDevelopment/electronic\\_applications/ctc.htm](http://ctep.cancer.gov/protocolDevelopment/electronic_applications/ctc.htm). All appropriate treatment areas should have access to a copy of the CTCAE. All reactions must first be reported in Rave on the “Adverse Events” Form and sent for rule evaluation at the time of the event. Adverse event data should not be entered in CTEP-AERS prior to entry in Rave for rules evaluation. Additional information about Rave-CTEP-AERS is available on the CTSU website (<https://www.ctsu.org>) under the “Resources” tab for each study.

In the rare occurrence when Internet connectivity is lost, a 24-hour notification is to be made to CTEP by telephone at [contact]. Once Internet connectivity is restored, the 24-hour notification phoned in must be entered electronically by the original submitter at the site.

For further information on the NCI requirements for SAE reporting, please refer to the ‘NCI Guidelines for Investigators: Adverse Event Reporting Requirements’ document published by the NCI.

**NOTE:** PRO-CTCAE data should not be used for determining attribution, dose modifications, or reporting serious adverse events.

Note: All deaths on study require both routine and expedited reporting regardless of causality. Attribution to treatment or other cause should be provided.

### 9.3.1 Late Phase 2 and Phase 3 Studies: Expedited Reporting Requirements for Adverse Events that Occur on Studies Under an IND/IDE ≤ 30 Days of the Last Administration of the Investigational Agent/Intervention 

#### FDA REPORTING REQUIREMENTS FOR SERIOUS ADVERSE EVENTS (21 CFR Part 312)

**NOTE:** Investigators **MUST** immediately report to the sponsor (NCI) **ANY** SAEs, whether or not they are considered related to the investigational agent(s)/intervention (21 CFR 312.64).

An AE is considered serious if it results in **ANY** of the following outcomes:

- 1) Death
- 2) A life-threatening AE
- 3) An AE that results in inpatient hospitalization or prolongation of existing hospitalization for ≥ 24 hours
- 4) A persistent or significant incapacity or substantial disruption of the ability to conduct normal life functions
- 5) A congenital anomaly/birth defect.
- 6) Important Medical Events (IME) that may not result in death, be life threatening, or require hospitalization may be considered serious when, based upon medical judgment, they may jeopardize the patient or subject and may require medical or surgical intervention to prevent one of the outcomes listed in this definition. (FDA, 21 CFR 312.32; ICH E2A and ICH E6).

**ALL SAEs** that meet the above criteria **MUST** be immediately reported to the NCI via CTEP-AERS within the timeframes detailed in the table below.

Grade 1-3 Timeframes	Grade 4-5 Timeframes
24-Hour notification, 10 Calendar Days	24-Hour notification, 5 Calendar Days

**NOTE:** Protocol-specific exceptions to expedited reporting of SAEs are found in the Specific Protocol Exceptions to Expedited Reporting (SPEER) portion of the CAEPR.

#### **Expedited AE reporting timeframes are defined as:**

- “24-Hour notification, 5 Calendar Days” - The SAE must initially be reported via CTEP-AERS within 24 hours of learning of the SAE, followed by a complete expedited report within 5 calendar days of the initial 24-hour report.

- “24-Hour notification, 10 Calendar Days” - The SAE must initially be reported via CTEP-AERS within 24 hours of learning of the SAE, followed by a complete expedited report within 10 calendar days of the initial 24-hour report.

SAEs that occur more than 30 days after the last administration of investigational agent/intervention and have an attribution of possible, probable, or definite require reporting as follows:

**Expedited 24-Hour notifications are required for all SAEs followed by a complete report**

- Within 5 calendar days for Grade 4-5 SAEs
- Within 10 calendar days for Grade 1-3 SAEs

For studies using nuclear medicine or molecular imaging IND agents (NM, SPECT, or PET), the SAE reporting period is limited to 10 radioactive half-lives, rounded UP to the nearest whole day, after the agent/intervention was last administered. Footnote “1” above applies after this reporting period.

Effective Date: August 30, 2024

•

**Additional Instructions or Exclusions to CTEP-AERS Expedited Reporting Requirements for Phase 2 and 3 Trials Utilizing an Agent Under a CTEP IND or non-CTEP IND:**

- All adverse events reported via CTEP-AERS (i.e. serious adverse events) should also be forwarded to your local IRB.
- Alliance A021502 uses a drug under a CTEP IND. The reporting requirements for investigational agents under a CTEP IND should be followed for all agents (any arm) in this trial.
- Grade 3 or 4 hematossuppression resulting in hospitalization does not require CTEP-AERS, but should be submitted as part of study results.
- All new malignancies must be reported via CTEP-AERS whether or not they are thought to be related to either previous or current treatment. All new malignancies should be reported, i.e. solid tumors (including non-melanoma skin malignancies), hematologic malignancies, myelodysplastic syndrome/acute myelogenous leukemia, and in situ tumors. In CTCAE version 5.0, the event(s) may be reported as one of the following: (1) Leukemia secondary to oncology chemotherapy, (2) Myelodysplastic syndrome, or (3) Treatment-related secondary malignancy. Whenever possible, the CTEP-AERS reports for new malignancies should include tumor pathology, history or prior tumors, prior treatment/current treatment including duration, any associated risk factors or evidence regarding how long the new malignancy may have been present, when and how the new malignancy was detected, molecular characterization or cytogenetics of the original tumor (if available) and of any new tumor, and new malignancy treatment and outcome, if available. New primary malignancies should be reported using study Form Notice of New Primary.
- Grade 1-3 nausea or vomiting resulting in hospitalization does not require AERS reporting, but should be reported via routine AE reporting.
- Grade 3 or 4 nausea or vomiting not resulting in hospitalization does not require AERS reporting, but should be reported via routine AE reporting
- Grade 1-3 oral mucositis resulting in hospitalization does not require AERS reporting, but should be reported via routine AE reporting
- Grade 3 or 4 oral mucositis not resulting in hospitalization does not require AERS reporting, but should be reported via routine AE reporting

- Grade 1-3 peripheral sensory neuropathy resulting in hospitalization does not require AERS reporting, but should be reported via routine AE reporting.
- Grade 3 peripheral sensory neuropathy not resulting in hospitalization does not require AERS reporting, but should be reported via routine AE reporting
- Grade 1-3 hand foot syndrome resulting in hospitalization does not require AERS reporting, but should be reported via routine AE reporting
- Grade 3 hand foot syndrome not resulting in hospitalization does not require AERS reporting, but should be reported via routine AE reporting
- Grade 1-3 hypersensitivity reaction resulting in hospitalization does not require AERS reporting, but should be reported via routine AE reporting.
- Grade 3 or 4 hypersensitivity reaction not resulting in hospitalization does not require AERS reporting, but should be reported via routine AE reporting
- Grade 1-3 dehydration resulting in hospitalization does not require AERS reporting, but should be reported via routine AE reporting
- Grade 3 dehydration not resulting in hospitalization does not require AERS reporting, but should be reported via routine AE reporting
- Grade 1-3 fatigue resulting in hospitalization does not require AERS reporting, but should be reported via routine AE reporting.
- Grade 3 or 4 fatigue not resulting in hospitalization does not require AERS reporting, but should be reported via routine AE reporting
- Treatment expected adverse events include those listed in [Section 10.0](#) and in the Comprehensive Adverse Events and Potential Risks list (CAEPR) below.
- CTEP-AERS reports should be submitted electronically.
- Pregnancy, as well as its outcome, must be reported as an AE in Rave and submitted for rules evaluation.
- Pregnancy loss
  - Pregnancy loss is defined in CTCAE as “Death in utero.”
  - Any Pregnancy loss should be reported expeditiously, as Grade 4 “Pregnancy loss” under the Pregnancy, puerperium and perinatal conditions SOC.
  - A Pregnancy loss should NOT be reported as a Grade 5 event under the Pregnancy, puerperium and perinatal conditions SOC, as currently CTEP-AERS recognizes this event as a patient death.
- A neonatal death should be reported expeditiously as Grade 4, “Death neonatal” under the General disorders and administration SOC.
- Death due to progressive disease should be reported as Grade 5 “Disease progression” under the system organ class (SOC) “General disorders and administration site conditions.” Evidence that the death was a manifestation of underlying disease (e.g. radiological changes suggesting tumor growth or progression: clinical deterioration associated with a disease process) should be submitted.
- Any death occurring within 30 days of the last dose, regardless of attribution to the investigational agent/intervention requires expedited reporting within 24 hours.

- Any death occurring greater than 30 days after the last dose of the investigational agent/intervention requires expedited reporting within 24 hours only if it is possibly, probably, or definitely related to the investigational agent/intervention.

